Both instruments are available for this study, and either / both will be used depending on anatomic considerations. This would be the first study in the UK assess the use of reflectance confocal microscopy in the diagnosis of MM and LM. If RCM is able to accurately diagnose melanoma in a significantly higher proportion of patients then Number of benign lesions Needed to Excise (NNE) to find a MM or LM might reasonably be reduced by 30% from its current value of approximately 10.

Aims

We propose to undertake a study to determine the diagnostic utility of using the RCM for the diagnosis of adult Malignant Melanoma (MM), Spitz naevi, Spitzoid melanoma and Lentigo Maligna (LM) in a tertiary referral centre as outlined by the recent NICE report (Nov 2015).

Study Design and Methods

Study Design

This is an observational, non-randomised, non-controlled, prospective cohort study to look at the efficacy of *in vivo* RCM as a diagnostic tool in the diagnosis of MM and LM.

Study Endpoints

The hypothesis of this study is that the use of RCM is would reduce the NNE prior to definitive treatment by at least 30% from the current value of approximately 10.

The secondary hypothesis is that the intra- & inter-observer agreement for interpreting the RCM images will have kappa scores 0.6 or greater (indicating good agreement).

Setting and recruitment

Patients will be recruited from the outpatient clinics of the Skin Care Network Barnet.

Participants

The number of true negative lesions examined in this study will be 654. It is anticipated that this will result in a total of 661 lesions being recruited. 10% of participants are expected to have more than one lesion sampled.

The result of biopsy for each lesion will not be known until after the lesion has been included in the study. Therefore lesions will be added to the study until the required number of true negatives has been included.

Recruits must fit the following criteria:

1. Age 18 years or older
2. Patient with a pigmented lesion recommended for excision because of suspicion of MM or LM.
3. Patient willing and able to give informed consent

Exclusion criteria

1. Recurrent MM or LM
2. Patient on immunosuppresants
3. Patient with significant co-morbidity or skin disease
4. Patient not suitable for diagnostic biopsy
5. Location of lesion unsuitable, inaccessible or impractical for scanning with RCM as determined by investigator

Informed Consent

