The primary hypothesis of this study is that the use of RCM is would reduce the number needed to excise (NNE) prior to definitive treatment by at least 30% from the current value of approximately 10. The secondary hypothesis is that the intra- & inter-observer agreement for interpreting the RCM images will have kappa scores 0.6 or greater (indicating good agreement).

The 95% confidence interval for the specificity and sensitivity will be calculated for both observers. The NNE will also be reported along with a 95% confidence interval.

To assess the inter-observer agreement the Kappa statistic will be reported alongside the proportion of agreements and disagreements.

Sample size calculation

The sample size has been determined in terms of the number of lesions examined, and assumes that lesions within a patient are independent.

Table 1 shows the relationship between the NNE and the specificity, assuming 100% sensitivity, for two values of the percentage positive in the population. For example if there are 5% positive lesions in the population of equivocal lesions and if NNE is to be 6, the specificity must be 74%. If the proportion of positive lesions is lower (2%) then a higher specificity is required to achieve each NNE value.

Table 1: Specificity as a function of NNE and N/P

% true P	N/P	NNE	pecificity
2%	49	6	90%
2%	49	7	88%
2%	49	8	86%
2%	49	10	82%
2%	49	15	71%
5%	19	6	74%
5%	19	7	68%
5%	19	8	63%
5%	19	10	53%
5%	19	15	26%

The numbers of lesions required to provide a lower confidence limit for the specificity which is no more than 3% lower than the estimate of specificity have been calculated for NNE values of 6, 7 and 8, for 5% and 2% true positives in the population, based on Table 1. Table 2 shows the results.

Table 2: Numbers of true positive and true negative lesions required for protocol HS-MAV-002

		NNE		
True positives:		6	7	8
5%	Specificity	75%	68%	63%
	True negative lesions required	564	654	701
2%	Specificity	90%	88%	86%
	True negative lesions required	271	317	362

The number of true negative lesions examined in this study will be 654. Therefore at anticipated prevalence, total number of lesions recruited to the study should be less than 700.

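### The sample size treats lesions from one patient as independent and no clustering adjustment is planned; if within-patient correlation is positive, simple intervals for specificity and NNE will be somewhat too narrow.

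*Combined protocol and SAP*

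**What the plan says.** All references are to the combined protocol and SAP.

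- **Sample size calculation.** The unit is the lesion, and the calculation "assumes that lesions within a patient are independent". The precision target is a "lower confidence limit for the specificity which is no more than 3% lower than the estimate of specificity". Table 2 gives 654 true negatives for 68% specificity (NNE 7, 5% positive), and the section adopts that figure: "The number of true negative lesions examined in this study will be 654".
- **Participants.** "10% of participants are expected to have more than one lesion sampled". The number of lesions from each such participant is not given, and no cap is stated. On the total: "It is anticipated that this will result in a total of 661 lesions being recruited".
- **Summary of statistical methods.** "The 95% confidence interval for the specificity and sensitivity will be calculated for both observers". An interval for NNE is also promised. No interval method, clustering adjustment or one-lesion-per-patient sensitivity analysis is described. Kappa is to be reported with the proportions of agreement and disagreement; no interval for it is mentioned.
- **Study Intervention.** Images are indexed by the subject's trial number, so the patient identifier needed for a clustered analysis is already recorded.

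**The concern.** The plan predicts clustered data and sizes the study as if there were none. Lesions on one patient share background skin and naevus pattern, and probably an imaging session, since imaging time is given per patient. The assessors also see the same age and sex for each of them. Correlated false-positive calls are therefore plausible, though the documents do not quantify them.

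With no method named for the analysis, a simple binomial interval is the likely default, and it would carry the independence assumption into the results. At stake is a modest overstatement of precision for specificity and for NNE, the two quantities on which the primary hypothesis depends.

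**Working it through.** **Step 1: reproduce the plan's figure.** Inputs from the Sample size calculation: specificity p = 0.68, margin d = 0.03. Formula: n = z²p(1−p)/d².

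- z = 1.645 (one-sided 95%): 1.645² × 0.68 × 0.32 / 0.03² = 654.1, the plan's 654.
- The other five cells of Table 2 reproduce in the same way from that table's specificities (564, 701, 271, 317, 362).
- z = 1.96 (two-sided 95%) gives 929, which does not match.

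So 654 contains no design effect.

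**Step 2: design effect.** DEFF = 1 + (Σm²/Σm − 1) × ICC. Per 100 patients, 90 give one lesion and 10 give m lesions. The 10% comes from the Participants section. The values of m and ICC are assumptions, as is the same lesion-count pattern among true negatives as overall.

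- m = 2: Σm²/Σm = 130/110 = 1.182
- m = 3: 180/120 = 1.5

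**Step 3: margin at 654 true negatives, specificity 68%.** Under independence the margin is 1.645 × √(0.68 × 0.32/654) = 3.00 points. With clustering it is 3.00 × √DEFF.

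| Lesions per multi-lesion patient | ICC | DEFF | Margin (points) | True negatives for 3 points | Coverage of a naive two-sided 95% interval |
|---|---|---|---|---|---|
| 2 | 0.1 | 1.018 | 3.03 | 667 | 94.8% |
| 2 | 0.5 | 1.091 | 3.13 | 714 | 93.9% |
| 2 | 1.0 (ceiling) | 1.182 | 3.26 | 774 | 92.9% |
| 3 | 0.1 | 1.05 | 3.07 | 687 | 94.4% |
| 3 | 0.5 | 1.25 | 3.35 | 818 | 92.0% |

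For ICC 0.1 to 0.5, the correct interval is 0.9% to 4.4% wider with pairs and 2.5% to 11.8% wider with threes.

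**Step 4: other specificities.**

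- At 76%, the meta-analysis value cited in Background, the margin is 1.645 × √(0.76 × 0.24/654) = 2.75 points under independence. With pairs it is 2.87 at ICC 0.5 and 2.99 at ICC 1, so the target is met throughout. With threes it is 2.95 at ICC 0.3 (2.75 × √1.15) and 3.07 at ICC 0.5 (2.75 × √1.25).
- In the 2% scenario Table 2 needs only 317 true negatives for NNE 7. Since 654/317 = 2.06, a design effect of up to about 2 could be absorbed.

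**Step 5: positives available for sensitivity.** 661 − 654 = 7. At 5% positive, 654/0.95 = 688, leaving about 34. If every positive is detected, a robust variance or a bootstrap returns a zero-width interval. An exact two-sided 95% interval still has a lower limit: 0.025^(1/7) = 59% for 7 of 7, or 0.025^(1/34) = 90% for 34 of 34.

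**The case against.** The strongest case against is that the assumption is disclosed and the effect is slight. The protocol speaks of a single target lesion and of 15 to 20 minutes' imaging per patient, so two lesions is the natural base case. There the margin moves by about a tenth of a point at ICC 0.5. A larger precision question sits beside this one: 654 rests on a one-sided limit, and a two-sided 95% interval at 654 has a half-width of 3.58 points. All of that stands, and it limits how much weight this point can bear. It does not remove it, because settling the one-sided question would leave the clustering unaddressed.

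A reader might also infer more than the documents support:

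- **That the plan prescribes an independence analysis.** It states independence only for the sample size. For the analysis the method is simply missing.
- **That the kappa interval will be too narrow.** No kappa interval is planned.
- **That a shared image assessor creates the clustering.** Intervals are calculated separately for each observer, so within any one interval every lesion has the same assessor.
- **That a large share of the information is lost.** Five lesions from every multi-lesion patient at ICC 0.5 would give a design effect of 1.71, making 654 lesions worth about 382. Nothing in the documents points to such counts. Without a cap they cannot be excluded, but they are extreme cases.
- **That sensitivity is affected to the same degree.** Few patients are likely to have two positive lesions.

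**Conclusion.** The point holds as a modest, conditional one. The sample size ignores clustering that the plan itself expects, and the interval method is unspecified. If within-patient correlation is positive, simple binomial intervals for specificity and NNE will be somewhat too narrow, and at 68% specificity 654 true negatives will fall slightly short of the 3-point margin: by 0.03 to 0.13 points with pairs at ICC 0.1 to 0.5 (0.26 at the ceiling), and by 0.07 to 0.35 points with threes over the same range.

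It would go too far to say that the precision target is necessarily missed. That depends on the sign and size of a correlation the documents do not give, on the lesions per patient, and on the specificity observed. The size rests on the assumed m and ICC; the absence of any design effect in 654 does not, since the figure reproduces exactly without one.

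**What to change.** 1. For specificity and NNE, compute the 95% intervals with patient as the cluster: GEE with independence working correlation and robust variance, or a patient-level bootstrap. Name the choice in the SAP before image reading begins.
2. For sensitivity, keep an exact binomial interval. Positives are few, and clustered methods collapse at 100% detection.
3. If an interval for kappa is reported, use a patient-level bootstrap.
4. In the Sample size calculation, replace the independence statement with the assumed number of lesions per patient and the resulting precision, for example about 3.1 points at 68% specificity with pairs and ICC 0.5. Report the observed distribution of lesions per patient.

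The cost is a short change to the SAP, minor programming and slightly wider intervals. No new data are needed. Accepting the slightly lower precision avoids raising recruitment. Holding 3 points with pairs at ICC 0.5 would need 714 true negatives, or 714/0.95 ≈ 752 lesions at 5% positive, above the section's projection of fewer than 700.

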The result of biopsy for each lesion will not be known until after the lesion has been included in the study. Therefore lesions will be added to the study until the required number of true negatives has been included. The resulting true positives will be used to estimate the sensitivity as a secondary endpoint.

Data management and analysis

The Clinical Record Forms (CRFs) must be completed, signed and dated by the Investigator or an authorised member of staff prospectively. The completed originals will be collected by the trials co-ordinator and held in the site file as source documents. It is the responsibility of the Investigator to ensure that CRFs have been completed correctly and that the data are accurate. Entries should be made in ballpoint pen and should be legible. Any errors should be crossed out with a single stroke, the correction inserted and the change initialled and dated. All missing and ambiguous data will be queried. The CRF may be amended as appropriate; this will not constitute a protocol amendment. The revised CRF should be used by all participating sites with immediate effect.

The data will be transferred anonymously to a password –secured electronic database. All patients will be pseudo-anonymised. Data will be stored in databases at Skin Care Network, and any copies to be taken off site (for example for statistical analysis or for analysis by the equipment provider) will be anonymised and will be protected by encryption and password. Access will be restricted to medical and research personnel, and appropriate support personnel. Specific trial information will be restricted to Investigators and collaborators. The trial co-ordinator will be responsible for the daily administration of the database.

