An initial interim analysis of the data will be planned after 25 patients to ensure the RCM images are of sufficient quality to continue and complete the study. Data validation will be co-ordinated under the supervision of the trial statistician once the recruitment target has been reached. The final analysis and publication of results will be undertaken after all patients have been recruited. The accrual period is estimated to be 12 months but will be continued until sufficient numbers are obtained for the study to reach significance. Once the dataset is complete, assessment of the RCM images by the blinded investigators will take place to allow statistical analysis of the primary and secondary endpoints, namely specificity, sensitivity and kappa statistics. Analysis of the final dataset is expected to take place within 6 months of completion of accrual. Publication is expected within 12 months of completing the trial.

Ethical Issues

The study proposal is subject to approval by the appropriate Ethics Committee and the host organisation's Medical Advisory Committee (MAC), and will adhere to Good Clinical Practice Guidelines. The study will be conducted according to the principles of the Declaration of Helsinki and in accordance with the Medical research Involving Human Subjects Act (WMO).

Amendments

Amendments are changes made to the research after a favourable opinion by the accredited Ethics Committees has been given. All amendments will be notified to the Ethics Committees that gave a favourable opinion.

A 'substantial amendment' is defined as an amendment to the terms of the Ethics Committee(s) application, or to the protocol or any other supporting documentation, that is likely to affect to a significant degree:

- the safety or physical or mental integrity of the subjects of the trial;
- the scientific value of the trial;
- the conduct or management of the trial; or
- the quality or safety of any intervention used in the trial.

All substantial amendments will be notified to the Ethics Committees and to the competent authority.

Non-substantial amendments will not be notified to the accredited Ethics Committees and the competent authority, but will be recorded and filed by the sponsor.

Annual Progress Report

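### Accrual is tied to reaching significance in one section and to 654 histology-negative lesions elsewhere, but 654 is a precision count for specificity that no test of the NNE stands behind

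*Combined protocol and SAP*

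**What the plan says.** Two statements govern when recruitment ends.

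- **Fixed count.** Participants and Sample size calculation set 654 true negative lesions, and "lesions will be added to the study until the required number of true negatives has been included". Sample size calculation adds that the "total number of lesions recruited to the study should be less than 700". Participants expects 661.
- **Significance.** Data management and analysis estimates 12 months of accrual, which "will be continued until sufficient numbers are obtained for the study to reach significance". It names no test. The Protocol Synopsis gives 18 months.

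The 654 is chosen so that the lower confidence limit for specificity is "no more than 3% lower than the estimate of specificity". The number of positives is not fixed: "The resulting true positives will be used to estimate the sensitivity as a secondary endpoint".

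Summary of statistical methods gives the primary hypothesis, that RCM would "reduce the number needed to excise (NNE) prior to definitive treatment by at least 30% from the current value of approximately 10". For its analysis the plan says only: "The NNE will also be reported along with a 95% confidence interval". It gives no interval method, significance level, power or rule comparing the interval with 10 or 7.

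On timing: "Once the dataset is complete, assessment of the RCM images by the blinded investigators will take place".

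**The concern.** A count chosen for the precision of specificity is described as the count at which the study becomes significant. The only numerical accuracy hypothesis concerns NNE, and NNE depends on the number of positives as well as on specificity. Nothing in the plan shows that the two end points coincide.

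Two things are at stake. First, the images are read only after the dataset is complete, so nobody can tell during accrual whether significance has been reached. The phrase could be acted on only after the analysis, by reopening recruitment when the result falls short. That would inflate the chance of a false positive claim. Second, a reader of the protocol may believe that 654 supports a significance claim about the 30% reduction, and no calculation in the plan does.

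**Working it through.** **1. Reproduce 654.** Inputs from Table 2 (5% positive, NNE 7): specificity 0.68, margin 0.03.

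n = z² × p(1 − p) / d² = 1.645² × 0.68 × 0.32 / 0.03² ≈ 654.

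The other Table 2 cells follow from the same formula (564, 701, 271, 317 and 362, to within one lesion of rounding). With z = 1.96 the result is 929, so the limit is one-sided 95%. Neither NNE 10 nor a power enters.

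**2. Link to NNE.** Table 1 uses NNE = (TP + FP)/TP at 100% sensitivity, so specificity = 1 − (NNE − 1)/(N/P). At 5% positive and NNE 7 this is 1 − 6/19 = 68.4%. The hypothesis means NNE of 7 or less (10 × 0.7).

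**3. Expected interval at the planning values.** Positives: 654/19 = 34.4. False positives: 6 × 34.4 = 206.5. RCM-positive lesions: 240.9. PPV = 1/NNE = 34.4/240.9 = 0.143.

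By hand, Wald on PPV: SE = √(0.1429 × 0.8571/240.9) = 0.0225. The limits are 0.143 ± 0.044, or 0.0987 to 0.1870, giving NNE 5.3 to 10.1. Clopper-Pearson gives 5.2 to 9.9 and Wilson 5.2 to 9.6. The Clopper-Pearson interval narrowly excludes 10 and includes 7.

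**4. Chance that the interval excludes 10.** The plan states no criterion, so I assume one: the upper two-sided 95% limit for NNE is below 10. Accrual stops at 654 negatives, positives are negative binomial, false positives are Binomial(654, 1 − specificity), and lesions are independent, as Sample size calculation assumes. Ranges span five interval methods: Wald, Clopper-Pearson and Wilson on PPV, log-NNE, and delta on NNE.

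| Share positive | Expected positives | Sensitivity / specificity | True NNE | Excludes 10 |
|---|---|---|---|---|
| 5% | 34 | 100% / 68.4% | 7 | 46-67% |
| 2% | 13 | 100% / 87.8% | 7 | 17-42% |
| 1.1% (7 of 661) | 7 | 100% / 93.6% | 7 | 8-32% |
| 10% | 73 | 100% / 33.3% | 7 | 80-90% |
| 5%, Background accuracy figures | 34 | 93% / 76% | 5.9 | 74-89% |

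In the first row the methods give Wald 46%, Clopper-Pearson 51%, Wilson 58%, log 59% and delta 67%. The last row's NNE is (0.93 + 19 × 0.24)/0.93 = 5.9.

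**5. Prevalence and sensitivity treated as known, as in Table 1.** Only specificity then varies: 68.4% ± 1.96 × √(0.684 × 0.316/654) = 68.4% ± 3.56 points. NNE = 1 + 19 × (1 − specificity) runs from 6.3 to 7.7. This excludes 10 and still includes 7.

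**6. The 30% claim itself.** With true NNE 7 at 5% positive, the upper limit falls below 7 in only 2-5% of studies. That is expected when the truth lies on the boundary, but it shows that the planned interval would not demonstrate a reduction of at least 30% at the planning value.

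**The case against.** The strongest reply is that the disputed phrase is loose wording for reaching the planned sample size. The sentence is about extending an estimated 12 months, the same section speaks of a recruitment target, and two other sections fix that target. Read as a whole, the plan stops at 654. This stands as far as it goes: a reader might infer result-driven optional stopping, and the documents do not support that, because the images are read only once the dataset is complete. What remains is that the phrase, taken literally, works only as a licence to reopen accrual, and it credits 654 with a property it was not given.

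A second reply is that sizing a diagnostic study on the precision of specificity is legitimate, that the Synopsis names specificity and sensitivity as the primary endpoint, and that NNE is merely reported with an interval. This also stands. The missing interval method and decision rule for NNE are missing detail, not an error in the 654.

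A third concerns the benchmark. Every enrolled lesion is already recommended for excision. If about 5% are positive, excising all of them gives NNE 1/0.05 = 20, not 10; a current NNE of 10 corresponds to about 10% positive, where the assumed criterion is met in 80-90% of studies. So a reader might infer that the study has only an even chance of success, or that accrual should be enlarged. Neither follows: the even chance belongs to one combination of prevalence, true NNE and an assumed criterion.

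**Conclusion.** The point holds as a conflict between two accrual statements and a mislabelled sample size. 654 gives a one-sided 95% limit for specificity within 3 points at 68%, and no test of NNE lies behind it, so reaching it does not mean significance is reached.

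The size of the gap depends on conditions the plan leaves open. Under the assumed criterion, with true NNE 7 and 100% sensitivity, the chance of excluding 10 runs from 8-32% at 1.1% positive to 80-90% at 10%. With prevalence and sensitivity taken as known, the expected interval lies well below 10. No single percentage is a property of 654. In both interval calculations at the planning values, 7 stays inside the interval, so excluding 10 would show some reduction but not one of at least 30%.

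The results assume independent lesions and read true negative as histology-negative. The point should be fixed in the text; it does not invalidate the design or call for more patients.

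**What to change.** 1. In Data management and analysis, replace the significance phrase with: *Accrual continues until 654 histology-negative lesions have been included and is not reopened on the basis of accuracy results.*
2. In Summary of statistical methods, describe NNE as an estimate with a 95% interval that reflects sampling of both positives and negatives, for example Clopper-Pearson on PPV = 1/NNE. State the expected interval (about 5.2-9.9 with about 34 positives). Do not present the 30% reduction as a significance claim.
3. Reconcile the 12-month accrual period in Data management and analysis with the 18 months in the Synopsis.

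This costs protocol wording only, with no additional patients or data. The one downside is that the stated precision for NNE will look less favourable than the 3-point margin for specificity suggests.
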